This pattern, however, can be disrupted by any stressful situation, such as severe pain from surgery, which has been linked to a progressive rise in cortisol levels both intraoperatively and in the early postoperative period.

Cytokines are group of low molecular weight proteins that modulate the systemic inflammatory response elicited by surgical intervention. Increased levels of proinflammatory cytokines, including interleukin-6 (IL-6) which is the main cytokine responsible for inducing the systemic changes, is an early features of acute injury. Interleukin-6 could be a good marker for research purposes that reflects and compares postoperative stress levels.

Spine surgeries are increasingly being performed as short-stay surgical procedures, and anterior cervical decompression and fusion is one such procedure (3).Postoperative incisional pain has been described as moderate in intensity, requiring opioid analgesics in most cases. Nonetheless, opioid-related side effects such as nausea, vomiting, and respiratory depression are undesirable in these patients who are at risk for airway problems due to surgical retraction or wound hematoma(4).

Regional anesthesia inhibits the stress response to surgery and can also influence postoperative outcomes. . The endocrinal stress response to the surgical operation is reduced as a result of inhibiting afferent impulses from the surgical site. Furthermore, a reduction in this type of stress response is seen as a key indicator of a successful regional block.

Intermediate cervical plexus block (CPB) is a safe and simple technique that has been shown to provide good pain relief through blocking all four cutaneous branches of the

cervical plexus, as well as sensory and motor branches (5). Not only Intermediate (CPB) is superior to superficial CPB in terms of effectiveness, but also is safer than deep (CPB) (6).

There is a paucity of evidence for the effect of bilateral cervical plexus block for anterior cervical spine surgeries. Prior research had employed recovery questionnaire score, 24-h opioid usage and length of hospital stay in assessment of cervical plexus block effectiveness (7), however estimating the effect of Intermediate (CPB) on stress biomarkers as serum cortisol and interleukin-6 has not been discussed yet.

Aim of the work

The aim of the present study is to investigate the effect of Bilateral Ultrasound-Guided intermediate cervical plexus Block combined with general anesthesia on the stress and inflammatory response in patients undergoing anterior cervical spine surgery (ACSS).

Objectives:

- *To compare between serum level of cortisol and interleukin-6 pre-operative and 24 hours post-operative in both groups.*
- *To identify Hemodynamics variables (mean arterial blood pressure and heart rate) peri-operatively.*
- *To assess the pain score during 1st 24 hours postoperative according to numeric pain rating scale (NPRS).*
- *To measure the incidence of complications within both groups.*

Hypothesis:

We hypothesize that intermediate cervical plexus block will offer a significant suppression of stress response and adequate post-operative analgesia in patients undergoing anterior cervical spine surgeries.

Ethical Considerations:

Our study will be conducted in Kasr El Aini Hospital, Cairo University after approval of the Research Ethics Committee. Full written informed consent will be obtained from the patients before inclusion in this study.

Methodology

Methodology

I. Study design:

A randomized controlled study.

II. Study setting and location:

The study will be conducted in the Neurosurgery operating rooms at Cairo University hospital.

III. Study population:

(66) Patients, aged from 18 to 65 years old, ASA physical status I-II, scheduled for anterior cervical spine surgery will be included in the study. Patients will be randomly allocated using concealed closed envelope method into one of two groups:

- Group A (n=33): will include the patients who will undergo bilateral ultrasound guided intermediate cervical plexus block after general anesthesia.*
- Group B (control group) (n=33): will include the patients who will undergo general anesthesia with conventional analgesia.*

IV. Eligibility Criteria

1. Inclusion criteria:

1. *ASA I & ASA II patients.*
2. *Age group: from 18 to 65 years old.*
3. *Patients undergoing anterior cervical discectomy or fixation.*
4. *Genders eligible for study: both sexes.*

2. Exclusion criteria:

- *Patient refusal.*
- *Patient Undergoing posterior fixation in addition to anterior.*
- *An allergy to local anaesthetics.*
- *Infection at block puncture site.*
- *Bleeding disorders (Coagulopathy: PTT > 40seconds, INR > 1.2, platelet count < 120 x 10³ / L.).*
- *Emergency surgeries & patients in sepsis.*

V. Study Procedures

1. Randomization:

Patients will be randomly allocated by a computer-generated table into one of the study groups; the randomization sequence will be concealed in sealed opaque envelopes

2. Study Protocol:

Patients will be subjected to systematic preoperative assessment including history taking, physical examination and review of the results of routine investigations. NPRS (numeric pain rating scale) will be explained to all candidates where zero corresponds to no pain, and 10 is indicative of the worst unbearable pain. Upon arrival to the preparation room: An 18-gauge intravenous (IV) cannula will be inserted into a peripheral vein. Patients will be premedicated by intravenous 0.01 mg/kg midazolam and 10mg metoclopramide. Patients will be then transferred to the operating room where basic monitoring, Electrocardiography (ECG), Non-invasive Blood Pressure (NIBP) monitor and pulse oximetry will be attached.

General anesthesia will be induced in a standardized way with intravenous propofol 2.5mg/kg, fentanyl 1 μ /kg and atracurium 0.5mg/kg. Anesthesia will be maintained by inhalational isoflurane and intravenous atracurium 0.1mg/kg/20min.

Group A: The patient will be placed in a supine or semi-sitting position, with the head turned slightly away from the side to be blocked to facilitate operator access. The skin is disinfected and a linear-array ultrasound probe (Siemens ACUSON X300 Ultrasound System) is placed on the lateral neck, overlying the sternocleidomastoid muscle at the level of its midpoint (approximately the level

of the cricoid cartilage), Once the SCM has been identified, the transducer is moved posteriorly until the tapering posterior edge is positioned in the middle of the screen. At this point, an attempt should be made to identify the brachial plexus and/or the interscalene groove between the anterior and middle scalene muscles. The cervical plexus is visible as a small collection of hypoechoic nodules (honeycomb appearance) immediately superficial to the prevertebral fascia that overlies the interscalene groove.

Once the plexus has been identified, the needle is passed through the skin, platysma, and investing layer of the deep cervical fascia, and the tip is placed adjacent to the plexus. . Following negative aspiration, 1–2 mL of normal saline is injected to confirm the proper injection site. Then after confirmation of safe needle position and absence of vascular spread, bupivacaine 0.25% (5–15 mL) is administered to envelop the plexus, and the block is repeated with the same technique on the opposite side.

(Figure 1).

[figure not shown]

Figure 1. *Cervical plexus (transverse view): desired distribution of local anesthetic (blue-shaded area) to nerve block the cervical plexus. Needle path: 1. ASM, anterior scalene muscle; CA, carotid artery; CP, cervical plexus; MSM, middle scalene muscle; SCM, sternocleidomastoid muscle.*

Group B: *Induction of general anesthesia as Group A, without performing intermediate cervical plexus block, intravenous morphine will be given in a dose of 0.1-0.2mg/kg to maintain intraoperative analgesia.*

All operations will be performed in the morning, taking into consideration circadian rhythm of hormone release. In both groups, venous blood samples to measure serum cortisol and interleukin-6 level will be collected before surgery as a baseline, then 24 hours post-operative. interleukin-6 is normally low and may be undetectable within 30-60 min after start of surgery while reaching maximum level at 24 hours post-operative.

During the intraoperative period; heart rate and mean arterial blood pressure will be recorded every 15 minutes throughout the surgery. Intravenous fentanyl bolus doses (0.5 µg/kg) will be adjusted to keep the HR and mean arterial blood pressure within 20% of the pre-induction values.

At the end of surgery, atracurium will be stopped and neuromuscular blockade will be reversed with intravenous neostigmine 0.04 mg/kg and 0.01 mg/kg atropine and endotracheal tube will be removed.

After operation, patients will be transferred to post anesthesia care unit (PACU) for complete recovery and monitoring. A standard postoperative analgesia regimen will be prescribed as intravenous paracetamol 1gm every 8 hours. Intravenous morphine 0.05 mg/kg will be given as a rescue analgesic dose if numeric analogue score was ≥ 3 . Metoclopramide 0.15 mg/kg IV will be prescribed for patients complaining of nausea or vomiting.

The maximum dose of morphine that will be given is 20 mg/24 hrs.

The block will be considered a failed block if the patient required more than two doses of rescue analgesia in the first hour postoperatively.

Measurement tools

- *Demographic data: age, sex, body mass index (BMI).*
- *Serum cortisol and interlukien-6 pre-operative and 24 hours post-operative.*
- *Hemodynamics {heart rate, arterial blood pressure (systolic, diastolic and mean blood pressure)} will be recorded at the following intervals: baseline reading , Intraoperative 15 minutes post-intubation (pre-block), 15 minutes after the block/administration of morphine and then every 15 minutes throughout the surgery, and postoperative at 1,6,12, 24 hours..*
- *NPRS score at 15, 30, and 60 min, 6, 12, 24 hours post-operatively.*
- *Number of patients in each group who need intraoperative additional analgesic doses of fentanyl and total fentanyl dose for each patient.*
- *Total postoperative analgesic requirements.*
- *Failure rate of the block (the block will be considered a failed block if the patient required more than two doses of rescue analgesia in the first hour postoperatively).*

VI. Study outcomes

1. Primary outcomes:

- *The serum cortisol level 24 hours postoperatively.*

2. Secondary outcomes:

- *The serum interleukin-6 24 hours postoperatively.*
- *Intraoperative hemodynamics {heart rate, arterial blood pressure (systolic, diastolic and mean blood pressure)}*
- *Intraoperative additional fentanyl requirements.*
- *NPRS score postoperative during 1st 24 hours. 15, 30, and 60 min, 6, 12, and 24 hours after surgery.*
- *Time to first postoperative analgesic request (duration of analgesia).*
- *Block failure rate.*
- *Incidence of complications. (Nerve injury, Hematoma formation, LA toxicity, intravascular injection.*
- *Block failure: The block will be considered a failed block if the patient required more than two doses of rescue analgesia in the first hour postoperatively.*

Statistical Analysis

Statistical Analysis

I. Sample size

Our primary outcome is the serum cortisol level 24 hours postoperatively. In a previous study, the serum cortisol level after 24 hours was 21.8 ± 4.7 micrograms per deciliter (mcg (ref) after lumbar fixation surgeries. We calculated a sample size that could detect a mean difference of 20% between both study groups. MedCalc Software version 14 (MedCalc Software bvba, Ostend, Belgium) was used to calculate the sample size 60 patients (30 Patient per group) at least were estimated to have a study power of 95% and an alpha error of 0.05. This number will be increased to 66 patients (33 patients per group) to compensate for possible dropouts.

Sample size calculation was performed guided by power of 95%, confidence level of 95 %.(8)

II. Statistical analysis

For data analysis, the Statistical Package for Social Science (SPSS) software, version 26 for Microsoft Windows (SPSS Inc., Chicago, IL, USA) will be used. The Chi squared test will be used to examine categorical data, which will be given as frequency (percent). The Shapiro-Wilk test will be used to verify for normality in continuous data, and the results will be provided as mean (standard deviation) or median (interquartile range) as appropriate. Depending on the data's normality, the unpaired t test or the Mann Whitney test will be used to assess it. Repeated measures will be examined using analysis of variance (ANOVA), with post-hoc pairwise comparisons using the Bonferroni tests. A P value less than 0.05 will be considered statistically significant.

References

References:

1. Arfanis K, Fioratou E and Smith A: Safety culture in anaesthesiology: Basic concepts and practical application. *Best Pract Res Clin Anaesthesiol* 25: 229-238, 2011.

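### The type of operation is eligible in two forms but is not a listed study variable and is not used in allocation or analysis, so any difference in cortisol between procedures would cost precision

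*Combined protocol and SAP*

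**What the plan says.** - **Eligibility (Methodology, IV).** The inclusion list takes "Patients undergoing anterior cervical discectomy or fixation". The only exclusion by type of operation is "Patient Undergoing posterior fixation in addition to anterior". No limit is set on the number of levels.
- **Allocation (Methodology, V.1 Randomization).** "Patients will be randomly allocated by a computer-generated table into one of the study groups". The sequence is concealed in envelopes. No strata are described.
- **Data collected (Measurement tools).** The baseline characteristics listed are "Demographic data: age, sex, body mass index (BMI"). Procedure, number of levels and duration of surgery are not on the list.
- **Planning values (Statistical Analysis, I).** "the serum cortisol level after 24 hours was 21.8 ± 4.7 micrograms per deciliter (mcg (ref) after lumbar fixation surgeries". The target is relative: "We calculated a sample size that could detect a mean difference of 20% between both study groups". The result is "60 patients (30 Patient per group) at least were estimated", which the plan says is "estimated to have a study power of 95% and an alpha error of 0.05". The total is then raised to 66 for dropouts.
- **Analysis (Statistical Analysis, II).** Continuous outcomes are compared by an unpaired t test or a Mann-Whitney test. No covariate is named.

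**The concern.** The primary outcome is a marker of the response to surgery, and IL-6 is included for the same reason. A discectomy alone and a longer fixation may well provoke responses of different size. The plan holds another influence on cortisol steady by scheduling all operations in the morning, but does nothing comparable for the operation itself.

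Two things are at stake. First, in a trial of 66 patients the arms can differ by chance in their share of fixations. The planned tables would not show a reader whether they did. Second, a mixed population may have a larger SD than the one used for planning, in which case the unadjusted test has less than the stated power.

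**Working it through.** **Inputs from the plan.** Mean 21.8 and SD 4.7 mcg/dL; difference 20%, so 0.20 × 21.8 = 4.36; power 95%; alpha 0.05. The plan does not say one- or two-sided; I take two-sided, because one-sided gives 26 per group and does not match.

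**Reproducing the plan's figure.**

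n per group = 2 × [4.7 × (1.960 + 1.645) / 4.36]² = 30.2

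This is 31 after rounding up, or 62 in all, against 60 stated. At 30 per group the power is 94.9% by the normal approximation and 94.2% by the noncentral t. The plan's arithmetic is therefore sound on its own inputs.

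**Assumptions, since the documents give no figures.** Half the patients have each procedure (p = 0.5, the mix that gives the largest variance). The SD within a procedure is 4.7. The mean gap *g* between procedures is 2.35, 4.7 or 7.05 mcg/dL (0.5, 1 or 1.5 planning SDs).

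**Total SD and power of the unadjusted test** (noncentral t, difference 4.36):

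Total SD = √[4.7² + p(1 − p)g²] = √[22.09 + 0.25g²]

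| Gap *g* (mcg/dL) | Total SD | Power, 30 per group | Power, 33 per group |
|---|---|---|---|
| 0 | 4.70 | 94.2% | 96.0% |
| 2.35 | 4.84 | 92.9% | 94.9% |
| 4.7 | 5.25 | 88.5% | 91.3% |
| 7.05 | 5.88 | 80.7% | 84.3% |

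**How likely is a visible imbalance?** Taking the number of fixations in each arm as binomial (33, 0.5), the chance that the arms differ by 6 or more is 17.5%. With arm sizes fixed at 33 and 32 to 34 fixations in total, it is 14% to 22%. A difference of 6 in 33 would move the unadjusted estimate by (6/33) × g = 0.43 / 0.85 / 1.28 mcg/dL, or 10% / 20% / 29% of the 4.36 target.

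**Is that shift additional to the power loss?** No. The difference between arms in the fixation share has SD √(2 × 0.25/33) = 0.123. At g = 4.7 the shift therefore has SD 0.123 × 4.7 = 0.58. The within-procedure standard error is 4.7 × √(2/33) = 1.157. Combining them, √(1.157² + 0.579²) = 1.294, which equals the standard error from the total SD, 5.25 × √(2/33). The imbalance is already inside the power column.

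**What adjustment would return.** A linear model with arm and procedure removes the between-procedure term, so the residual SD goes back to 4.7 on 60 − 3 = 57 degrees of freedom. With arms balanced on procedure, power at 30 per group is again about 94%, slightly less if they are not.

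**The case against.** The strongest reply is that nothing here is invalid. Unstratified randomisation protects the type I error and gives no systematic bias; chance imbalance is part of what the standard error measures. That stands. A reader might infer that a cortisol result would be biased or uninterpretable, and the plan does not support that reading.

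A reader might also infer that the planning SD contains no between-procedure variation because it comes from one kind of operation. The documents do not show this. The sample-size section says only that the values follow lumbar fixation, in the plural and with no limit on levels, and the source itself is not available here. Its SD may already include variation in extent. The SD in anterior cervical surgery could be smaller or larger than 4.7, so using 4.7 as the within-procedure value is an assumption.

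The magnitude is open to challenge too. The 50:50 mix is the least favourable one, and the largest gap, 7.05, exceeds the whole target difference of 4.36. Even there power stays above 80%. At the smallest gap the loss is about one percentage point.

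Finally, it would go too far to say that imbalance could never be seen. Staff must know the procedure to apply the eligibility criteria, and haemodynamic readings every 15 minutes give a rough duration of surgery. What stands is narrower: procedure is not a listed study variable and no analysis uses it.

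**Conclusion.** The point holds as a matter of precision and reporting, not validity. Eligibility is mixed, and the listed data, the allocation and the primary comparison all leave procedure out. If 24-hour cortisol differs by procedure, the unadjusted test loses power: from 94% to about 93% / 88% / 81% at 30 per group, or from 96% to about 95% / 91% / 84% with all 33 analysed. These figures rest on the assumed mix, within-procedure SD and gaps, none of which the documents supply.

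The chance shift from imbalance should not be counted as a second harm, and the planned 60 is not shown to be wrong. Whether lumbar values carry over to cervical surgery at all is a separate question. It bears on power directly, and the plan does not argue it. This is a cheap improvement worth making, of minor weight.

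**What to change.** 1. Add two fields to the baseline data, completed before randomisation: planned procedure (discectomy alone or fixation) and planned number of levels. Tabulate both by arm.
2. Prespecify a linear model for 24-hour cortisol, and likewise for IL-6, with arm and planned procedure as terms. This replaces the unadjusted t or Mann-Whitney test for these two outcomes. Use the planned procedure, not the one performed, so that the covariate cannot be affected by allocation.
3. State in the sample-size section that the 95% power is conditional on an SD from lumbar fixation, and show power over a range of SDs.

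Stratifying the envelopes by planned procedure is optional. In 66 patients it means a second envelope series, and prespecified adjustment recovers most of the precision without it. If it is wanted, it has to be set up before enrolment; the items above are worth doing even if the envelopes already exist.

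The cost is two data fields and one degree of freedom, with no extra patients or blood samples.

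### Pain and regular opioid use before surgery are not recorded, so the pain and analgesic secondary outcomes cannot be checked or adjusted for them; separately, the allergy exclusion does not match the drugs the protocol requires

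*Combined protocol and SAP*

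**What the plan says.** **Who is eligible.** The surgical inclusion criterion in Eligibility Criteria is "Patients undergoing anterior cervical discectomy or fixation". The exclusions are refusal, added posterior fixation, "An allergy to local anaesthetics", infection at the puncture site, bleeding disorders, and "Emergency surgeries & patients in sepsis". Pre-existing pain, regular opioid use and opioid allergy do not appear.

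**What is recorded beforehand.** Under Study Protocol, the preoperative work-up is described as "including history taking, physical examination and review of the results of routine investigations", and "NPRS (numeric pain rating scale) will be explained to all candidates". No score is requested at that point. The baseline data in Measurement tools are age, sex, BMI, haemodynamics, cortisol and interleukin-6.

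**What is recorded afterwards.** Measurement tools lists "NPRS score at 15, 30, and 60 min, 6, 12, 24 hours post-operatively". Rescue in the common postoperative regimen depends on an absolute score: "Intravenous morphine 0.05 mg/kg will be given as a rescue analgesic dose if numeric analogue score was ≥ 3". A block counts as failed if a third rescue dose is needed within the first postoperative hour.

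**Analysis.** The Statistical analysis section names the unpaired t test or Mann-Whitney test, the Chi squared test, and ANOVA for repeated measures with Bonferroni comparisons. No covariate is named, and Randomization names no stratification factor.

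**The concern.** Cortisol, interleukin-6 and haemodynamics each have a preoperative reading; pain does not. NPRS, time to first request, total analgesic requirement and block failure are therefore all read without knowing where the patient started. Someone who arrives with a score of 3 or more, or who takes opioids regularly, may reach the rescue threshold for reasons unrelated to how well the incision is blocked.

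Between arms, this costs precision and leaves any chance imbalance invisible. Within Group A, it clouds the block failure rate, because no recorded variable separates a technical failure from habitual pain or tolerance. These outcomes are secondary, but adequate postoperative analgesia is half of the stated hypothesis.

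A separate matter is that the allergy exclusion covers only the block drug. As written, a patient who cannot be given morphine may be randomised, yet could not receive Group B's allocated analgesic, or the rescue drug in either arm.

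**Working it through.** **1. The plan's own figure.** Inputs from Sample size: mean 21.8, SD 4.7, difference 20%, power 95%, alpha 0.05 (two-sided assumed).

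- Difference = 0.20 × 21.8 = 4.36 mcg/dL.
- n per group = 2 × [4.7 × (1.960 + 1.645) / 4.36]² = 30.2, rounded up to 31. The plan states 30.
- Power at 30 per group is 94.9% (normal approximation).

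The figure reproduces to within one patient per group. It concerns 24-hour cortisol and does not depend on baseline pain, so the rest of this check applies to the secondary outcomes only.

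**2. Precision from a baseline score.** The documents give no correlation between preoperative and postoperative NPRS; r = 0.3 to 0.5 is an assumption. A linear covariate removes r² of the residual variance, equivalent to 1/(1 − r²) − 1 more patients.

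| r | Variance removed | Equivalent extra patients |
|---|---|---|
| 0.3 | 9% | 1/0.91 − 1 = 10% |
| 0.5 | 25% | 1/0.75 − 1 = 33% |

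**3. Chance imbalance at 33 per arm.** Let p be the share of patients in pain or on regular opioids before surgery. The documents give no figure; p = 20% to 40% is assumed. The between-arm difference in that share has mean 0 and SD √[2p(1 − p)/33]. Tail probabilities are exact, for two independent binomials.

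| p | SD (percentage points) | P(difference ≥ 15 points) | P(difference ≥ 20 points) |
|---|---|---|---|
| 20% | 9.8 | 16% | 4% |
| 40% | 12.1 | 26% | 10% |

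For regular opioid use alone, if 15% are users (assumed), 0.15 × 66 ≈ 10 patients are affected. A split of 7 to 3 or more uneven then has probability 30% (hypergeometric).

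**4. Effect on the NPRS comparison.** If affected patients score 1 to 2 points higher (assumed), 95% of randomisations shift the difference in means by no more than 1.96 × SD × shift:

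- p = 20%, 1 point: 1.96 × 0.098 × 1 = 0.19
- p = 40%, 2 points: 1.96 × 0.121 × 2 = 0.47

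The shift is about 0.2 to 0.5 points on the 0-10 scale, in either direction, averaging zero.

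**5. Block failure.** Only Group A has a block, so the rate has no randomised counterpart and randomisation gives it no protection. Its definition counts rescue doses, and rescue depends on an absolute score, so the block, prior pain and tolerance all feed one number.

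**6. Allergy criterion against required drugs.** Eligibility Criteria screens for allergy to local anaesthetics, which only Group A receives under the protocol. Study Protocol gives morphine intraoperatively in Group B and as rescue without distinction by group. The two passages do not match.

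**The case against.** A reader might infer that pre-existing pain and tolerance are confounded with the block effect. The documents do not support that. Allocation is computer-generated and concealed, so both factors balance in expectation and the between-arm comparisons are not systematically biased. The likely distortion from imbalance is also modest: a 7 to 3 split is 4/33 = 12 percentage points, or 0.12 to 0.24 NPRS points under the shifts assumed above. This objection stands, and limits the point to precision, undetected imbalance and the reading of block failure.

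A reader might also infer that the allergy gap contaminates the pain scores, or that the resulting deviations would be confined to Group B. Neither follows. The gap is an eligibility mismatch, and a Group A patient could also deviate once rescue is due. History taking may reveal an allergy or opioid use, but nothing makes the answer an eligibility rule or trial data.

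Three further objections are fair.

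- The documents do not say how common pain or opioid use is before this surgery; the text cited in the introduction concerns postoperative incisional pain. Every prevalence used here is an assumption.
- The r² gain belongs to a linear adjusted mean. The plan allows Mann-Whitney, and rescue itself alters later scores, so the full gain may not be realised.
- A habitual score of 3 does not alone make a failed block; the need must persist to a third dose within an hour. This makes misclassification less frequent but does not make it detectable.

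Excluding regular opioid users would narrow applicability and is not needed to meet the concern.

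**Conclusion.** The point holds as a precision and interpretability weakness in secondary outcomes. No baseline NPRS or opioid use is recorded and no adjustment is planned. The cost is roughly 9-25% of residual NPRS variance if r is 0.3-0.5. There is also a 16-26% chance of an unseen imbalance of 15 points or more if 20-40% of patients are affected. Both ranges rest on assumptions from outside the documents. Block failure is the one outcome where pre-existing pain and tolerance enter without protection from randomisation. The primary outcome and its sample size are untouched.

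The allergy mismatch is a separate inconsistency between sections, with no estimable size. It should not be read as a cause of the pain-outcome problem.

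**What to change.** 1. When the NPRS is explained preoperatively, record a score and regular opioid use (yes/no, with the sponsor defining regular use). Add both to Measurement tools and report them by arm.
2. In Statistical analysis, specify that postoperative NPRS is compared with a model adjusted for baseline NPRS and opioid use, for example ANCOVA at a named time point or a repeated-measures model over all six.
3. Report block failure in Group A by baseline opioid use and baseline pain, as description only, since 33 patients will not support more.
4. Separately, reconcile the allergy exclusion with the drugs named in Study Protocol, so that every randomised patient can receive either allocation and the rescue drug. How this is done is for the sponsor to decide.

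The cost is two data items at a contact that already takes place, and slightly more analysis. The adjusted model addresses NPRS only; for rescue use and time to first request, reporting baseline by arm at least lets a reader judge imbalance. Item 4 costs a small edit to the eligibility text. These baseline values cannot be reliably recovered after surgery, so the change should come before enrolment.

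### The platelet exclusion limit is printed per litre; read literally, that part of the coagulopathy criterion would exclude no one, so the unit needs checking and probably correcting

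*Combined protocol and SAP*

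**What the plan says.** The exclusion list under IV. Eligibility Criteria names bleeding disorders and describes them in parentheses by PTT, INR and platelet count. It begins "Bleeding disorders (Coagulopathy: PTT > 40seconds, INR > 1.2" and the last two limits read "INR > 1.2, platelet count < 120 x 10³ / L". This is the only platelet limit in the document. No reference range, second unit or platelet data are given against which to check it.

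V. Study Procedures (2. Study Protocol) describes the preoperative assessment as "history taking, physical examination and review of the results of routine investigations", which is where such a limit would naturally be applied. For Group A the block is bilateral: "the block is repeated with the same technique on the opposite side". VI. Study outcomes lists among the secondary outcomes "Incidence of complications. (Nerve injury, Hematoma formation, LA toxicity, intravascular injection".

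**The concern.** An eligibility limit has to be usable as written, because eligibility checks and deviation reports are made against the text. A platelet limit expressed as thousands per litre is far below any count that a patient coming to elective surgery could plausibly have. As printed, it cannot separate eligible from ineligible patients.

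What is at stake is safety screening before an invasive procedure. Group A patients receive an injection on each side of the neck, haematoma is one of the trial's own complication outcomes, and the introduction notes that these patients are at risk of airway problems from wound haematoma. PTT and INR do not stand in for a platelet count: a patient with a low count and normal PTT and INR passes both of those limits. If one screener applies the printed unit and another silently substitutes a different one, the same patient could be handled differently.

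**Working it through.** **Input from the plan.** Platelet limit as printed: below 120 x 10³ per L (IV. Eligibility Criteria, 2. Exclusion criteria). This is a stated limit, not a derived figure, so there is no calculation in the plan to reproduce.

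**Step 1. Convert the printed limit.** With 1 L = 10⁶ µL:

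- 120 x 10³ per L = 120,000 per L
- 120,000 / 10⁶ = 0.12 per µL
- 120,000 / 10⁹ = 0.00012, so the limit is 0.00012 x 10⁹ per L

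**Step 2. Compare with the same digits per µL.** 120 x 10³ per µL x 10⁶ µL per L = 120 x 10⁹ per L. The ratio to the printed limit is 120 x 10⁹ / 120 x 10³ = 10⁶. This comparison only measures the size of the discrepancy; it does not say what the limit should be.

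**Step 3. Ask who would be excluded under the literal reading.** The plan gives no platelet data, so the counts below are assumptions chosen to span a wide range. Ratio = (count per µL x 10⁶) / 120,000.

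| Assumed count (10³ per µL) | Per litre | Ratio to printed limit |
|---|---|---|
| 1 | 1 x 10⁹ | about 8,300 |
| 10 | 10 x 10⁹ | about 83,000 |
| 50 | 50 x 10⁹ | about 417,000 |
| 100 | 100 x 10⁹ | about 833,000 |

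None of these falls below the printed limit, so the platelet part of the criterion excludes none of them.

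**Step 4. Check for knock-on effects.** The sample size rests on 24-hour cortisol (mean 21.8, SD 4.7), a 20% difference, 95% power and alpha 0.05. No platelet figure enters it, and none enters the analysis section. Correcting the unit changes no statistical figure.

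**Step 5. Look at how units survive elsewhere in the text.** Two other places carry a micro sign:

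- Induction dose: "fentanyl 1 μ /kg and atracurium 0.5mg/kg". The micro sign is present; the mass unit after it is missing.
- Intraoperative boluses: "Intravenous fentanyl bolus doses (0.5 µg/kg". The unit is intact.

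Both micro signs survived. The first example still shows that units in this text are not always complete.

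**The case against.** The strongest objection is that the plan may contain no error. There is a blank between the slash and the L, exactly where a micro sign would sit, and the induction dose shows that units in this text can be incomplete. A symbol lost in reading the PDF is not a fault of the plan. Part of this stands: the documents cannot settle it, and it limits confidence. Against it, both other micro signs came through, and the induction dose lacks the mass unit rather than the micro sign. The blank is also weak evidence, since there is one on each side of the slash and a stray space occurs elsewhere, before the full stop after the rescue-analgesia pain score.

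The second objection is that clinicians reviewing routine blood results would probably read the limit in their laboratory's usual unit. That is likely, but it is a judgement that the documents do not state, and it does not make the printed criterion correct.

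Third, other safeguards remain. Bleeding disorders as such are excluded, the PTT and INR limits work as printed, and entry is restricted to ASA I and II. These narrow the group affected. They do not replace a platelet limit for a patient whose only abnormality is a low count.

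A reader might infer more than the text supports:

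- **That the bleeding-risk screen as a whole excludes nobody.** The documents do not support this. The literal reading disables only the platelet part, and nothing shows how screeners would apply it.
- **That sites would apply eligibility inconsistently.** The plan names one setting, the neurosurgery operating rooms at Cairo University hospital. Only differences between screeners are possible.

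**Conclusion.** The point holds in a limited form. As printed, the platelet limit is 0.12 per µL, 10⁶ times lower than the same digits per µL. Read literally, that part of the coagulopathy exclusion would exclude no one. The most probable explanation is a unit slip.

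The conclusion rests on two assumptions: that the source document also prints the unit per litre, and that no candidate has a count anywhere near 0.12 per µL. The second is safe. The first is unverified, and if the source prints a micro sign the point falls away.

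Severity is minor to moderate: the limit bears on safety before bilateral neck injections, but other exclusions still act and no sample size, power or analysis figure is affected. Confidence is moderate because of the open question about the source text.

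**What to change.** 1. Check the unit in the source document. If it carries a micro sign, nothing needs to change.
2. If it reads per litre, the sponsor should confirm the intended limit and restate it once, in the unit the hospital laboratory reports. The value is a clinical decision for the sponsor, and none is suggested here.
3. If any patients have already been screened, check their recorded counts against the corrected limit. The plan is written prospectively and reports no screening, so this step may not apply.

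The cost is a one-line correction. The plan already calls for review of routine preoperative investigations; if these include a platelet count, which the plan does not spell out, no new measurement is needed. Any additional exclusions should be few, though the plan gives no data from which to estimate the number.
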